## 11.6 Excessive Toxicity – Criteria for Stopping and Interim Safety Analysis

In case of excessive toxicity, safety-stopping rules will be used. An acceptable toxicity rate will be assumed at 0.20. The study will be stopped based on an unacceptable excessive toxicity rate of 0.40. A sequential probability ratio test will be used where a likelihood ratio of 8 in favor of an excessive toxicity rate of 0.40 (vs. 0.20) provides sufficient evidence to stop the study due to excessive toxicity. Data will be continuously reviewed for excessive toxicity and statistical analysis performed if excessive toxicity is suspected. The table below provides the minimum number of patients exhibiting excessive toxicity that will trigger statistical analysis.

Total number of treated patients	Number of Patients observed with excessive toxicity
3	≥2
4-5	≥3
6-7	≥4
8-9	≥5
10-11	≥6
12-13	≥7
14-16	≥8
17-18	≥9
19-20	≥10

Version Date: 13AUG2018 Confidential Page 41 of 51

21-23	≥11
24-25	≥12
26-28	≥13
29-30	≥14
31-33	≥15
34-35	≥16
36-38	≥17
39-40	≥18

Ramucirumab will be held for drug related adverse events Grade  $\geq 3$  until recovery to Grade  $\leq 1$  and then resumed with a lower dose level -1 (6 mg/kg). If the Grade  $\geq 3$  related adverse event does not resolve within 4 weeks of holding treatment, the subject will be taken off study treatment.

In the case of prolonged or medically concerning Grade 2 toxicity related to the chemotherapy combination, treatment will be interrupted until recovery to Grade  $\leq 1$ , at which time treatment will be resumed at the same dose. If the adverse event does not resolve in or within 2 weeks with medical intervention, then the subject will be taken off study treatment.

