## 11.6.1 Excessive Toxicity

Excessive toxicity is defined as any adverse event that meets the following criteria:

- Any grade 3 or higher adverse event or an adverse event that leads to discontinuation of study therapy.
- The adverse event must be possibly, probably or definitely related to any of the study treatments (Ramucirumab, Oxaliplatin, Irinotecan, 5-FU)
- The adverse event occurs in the first four weeks of treatment
- The adverse event grade does not diminish to grade 1, four weeks after dose modification or dose delay. AE must have been adequately treated (e.g. nausea, vomiting, hematologic toxicities)

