## 11.6.2 Interim Safety Analysis

The study will be closed to accrual and an interim safety analysis conducted after ten subjects are accrued to each arm. If the following rates of selected toxicities listed below are observed within the first cycle of treatment (four weeks), the regimen (Ramucirumab, Oxaliplatin, Irinotecan, 5-FU) will be considered toxic and the trial will be stopped.

Adverse Event (≥ grade 3)	Toxicity Rate (n/10 subjects)
Febrile Neutropenia	2/10
Peripheral Motor or Sensory Neuropathy	3/10
Hypertension	3/10
Life Threatening Thromboembolic Event	3/10
GI Perforation	2/10
Hemorrhage, Bleeding	2/10

Version Date: 13AUG2018 Confidential Page 42 of 51

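### Section 11.6 counts patients still inside the toxicity window as toxicity-free, so the printed table can trigger its analysis late or miss it

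*Combined protocol and SAP*

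**What the plan says.** Section 11.6 describes a sequential probability ratio test of a toxicity rate of 0.40 against 0.20, with a likelihood ratio of 8 as sufficient evidence to stop. On timing it says: "Data will be continuously reviewed for excessive toxicity and statistical analysis performed if excessive toxicity is suspected". A table then gives "the minimum number of patients exhibiting excessive toxicity that will trigger statistical analysis". Its two columns are "Total number of treated patients", running from 3 to 40, and "Number of Patients observed with excessive toxicity".

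Section 11.6.1 defines the event. It must be related to study treatment, start in the first four weeks of treatment, and satisfy a persistence condition: "The adverse event grade does not diminish to grade 1, four weeks after dose modification or dose delay". The synopsis words the definition differently. It refers to toxicity in the first four weeks after enrollment, mentions dose modification, and has no separate four-week persistence requirement.

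Section 11.6.2 adds a separate look at listed toxicities during the first cycle: "The study will be closed to accrual and an interim safety analysis conducted after ten subjects are accrued to each arm".

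Neither the synopsis nor section 11.6 with its subsections limits the denominator to patients whose toxicity window is complete.

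**The concern.** The test compares two rates of a completed yes/no outcome. A patient enters the denominator at first dose but can enter the numerator only once an event has occurred and, under 11.6.1, has failed to resolve. Until then the patient is scored as a non-event although the outcome is unknown. With continuous review and continuing accrual, some patients are always in that state, so the observed rate is biased downward and the bias runs only toward not triggering. What is at stake is the chance that a regimen with the protocol's own unacceptable toxicity rate is flagged while patients are still being entered.

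**Working it through.** **Inputs from the protocol.** Rates 0.20 and 0.40, ratio 8, the trigger table and continuous review (11.6); onset in weeks 0 to 4 plus a further four weeks for non-resolution (11.6.1); accrual closed after ten per arm (11.6.2); 85 patients over 24 months (11.10).

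**Likelihood ratio.** For x events in n patients, LR = (0.4/0.2)^x × (0.6/0.8)^(n−x) = 2^x × 0.75^(n−x). Each patient scored as event-free multiplies it by 0.75.

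**The plan's own table.** Taking the smallest x with LR ≥ 8 reproduces the printed count in only 5 of 38 rows (n = 6, 8, 9, 10, 11). At n = 20 a ratio of 8 needs 8 events and the table needs 10; at n = 40 it needs 14 and the table needs 18. That mismatch is a separate fault, but it means the table and the ratio test must be assessed separately here.

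**Patients pending at any look.** Accrual is 85/24 = 3.54 a month. Four weeks is about 0.92 months, so 3.54 × 0.92 ≈ 3.3 patients are within 4 weeks of first dose; for 8 weeks the figure is about 6.5. The second is an upper figure, since a patient with no qualifying onset by week 4 is already known to be event-free.

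**Example.** Six events in 10 complete patients: LR = 2^6 × 0.75^4 = 20.2, and the table (6 or more at n = 10) triggers. Add 6 pending patients, n = 16: LR = 2^6 × 0.75^10 = 3.6, and the table needs 8. The evidence is the same but nothing is triggered.

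**Simulation.** Assumptions: Poisson accrual at 3.54 a month with arms pooled; toxicity becomes known uniformly over days 0–28 (4-week reading) or days 28–56 (8-week reading); review continues until the 40th patient is treated; accrual is held after patient 20 for one full window. The protocol does not state the length of the hold. Probability of crossing at a true rate of 0.40:

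| Rule | Window | All treated | Window-complete |
|---|---|---|---|
| Printed table | 4 weeks | 0.53 | 0.64 |
| Printed table | 8 weeks | 0.33 | 0.64 |
| Ratio of 8 | 4 weeks | 0.81 | 0.82 |
| Ratio of 8 | 8 weeks | 0.72 | 0.80 |
| Printed table, Arm A only, hold at 10 in the arm | 4 weeks | 0.59 | 0.65 |
| Printed table, Arm A only, hold at 10 in the arm | 8 weeks | 0.47 | 0.64 |

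If the table must be met and the ratio must also reach 8, the pooled figures with the hold are 0.48 (4-week) or 0.34 (8-week) on all treated, against 0.57 on complete patients.

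**Ratio test over all 85 patients, with the hold.** All treated against complete: 0.97 against 0.97 (4-week) and 0.95 against 0.97 (8-week). Median number treated at stopping: 19 against 18, and 20 against 20.

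**At a true rate of 0.20.** The printed table's false-trigger rate is about 0.06 (4-week) or 0.01 (8-week) on all treated, against 0.13 on complete patients. For the ratio of 8, to 40 treated, it is about 0.03 to 0.06 against 0.08.

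**The case against.** The strongest reply is that the table does not stop the trial. It prompts a statistical analysis, the stopping evidence is the ratio of 8, and the denominator of that calculation is not stated. Analysis may also follow whenever excessive toxicity is suspected. A reader might infer that the rule as a whole stops too late or never. The documents do not support that: only the table ends at 40, and the ratio test carries no such limit. Run over all 85 patients with the hold, it loses about 0 to 2 points with little delay. What remains is that a missed table entry removes the protocol's stated prompt for the analysis, and a ratio computed on all treated patients is deflated in the same way.

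Second, accrual closes after ten per arm, which lets those patients mature. This helps, but modestly: for the printed table with an 8-week window, the trigger probability rises from about 0.29 without the hold to about 0.33 with it. A reader might also infer that the 11.6.2 look itself scores immature patients as safe. Nothing there says so. Accrual is closed at that point, and the toxicities are those of the first cycle. Only the timing of the look could be clearer.

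Third, the large drops depend on the 8-week reading, pooled counting and the printed table, whose complete-data trigger probability is only 0.64 because its counts are stricter than a ratio of 8 from n = 12. This stands. The synopsis makes the 8-week reading contestable, and the documents do not say whether arms are pooled.

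**Conclusion.** The point holds in limited form and should be corrected. Followed literally, 11.6 scores patients with unknown status as toxicity-free, and the printed table then triggers late or is missed. The direction does not depend on the assumptions; the size does. At a true rate of 0.40 and to 40 treated, the table loses about 11 points (0.64 to 0.53) on a 4-week window and about 31 points (0.64 to 0.33) on an 8-week window with arms pooled. If only Arm A is counted, the losses are about 6 and 17 points. The ratio-of-8 test to 40 treated loses about 1 and 8 points. A failure to trigger at all is a property of the printed table, not of a ratio test carried through the whole trial. These figures rest on accrual at the planned rate, uniform timing of recognition and a hold lasting one window.

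**What to change.** In 11.6, define the denominator of both the trigger table and the likelihood-ratio calculation as patients who have completed the toxicity observation window, and count events among those patients. State explicitly how an event already confirmed in a patient still inside the window is handled. The choice matters: read literally, such an event waits for the window to close, whereas admitting events at once while event-free patients wait biases the count upward and gives a table false-trigger rate of about 0.23 at a true rate of 0.20 (pooled).

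Reconcile the toxicity definitions in the synopsis and 11.6.1 so that the window has one length, and say whether counting is pooled or by arm. In 11.6.2, clarify only that the look is made once the ten patients per arm have completed cycle 1.

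These are wording changes. The statistical cost is that false triggers at 0.20 return to each rule's complete-data level: about 0.13 for the printed table (from 0.01 or 0.06) and about 0.08 for the ratio of 8 (from 0.03 to 0.06). The lower figures arise only because unknown outcomes are counted as safe.

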# STATISTICAL CONSIDERATIONS

We aim to test the null hypothesis of PFS at 6 months. Using a one-sided log-rank test we have estimated a sample size of 85 patients (43 in one and 42 in another arm) which will provide 80% power under a type 1 error of 20%. This is an estimation on 24 months accrual and 9 months follow up after accrual for the primary endpoint. Sample size may increase to 95 to account for a 10% drop out rate.

The primary endpoint of this clinical trial is PFS. PFS is defined as the time from enrollment to the time of progression or death. An interim analysis with Kaplan Meier method and Logrank test will be conducted after 23 subjects have been enrolled in each arm and followed up for 9 months. The trial will stop if it detects a significant difference of 3 months in PFS between the study arm-mFOLFIRINOX/RAM, as compared to the standard arm-mFOLFIRINOX at the significance level of 0.0013 according to the O'Brien-Fleming approach. Otherwise the trial will continue until the targeted sample size has been completed.

RR, PFS and OS will be reported with 95% confidence intervals. Response is defined as a complete or partial response according to CT/MRI evaluations based on RECIST 1.1 criteria. Toxicity will be graded using CTCAE v4

**Early stopping:** In the case of excessive toxicity, safety-stopping rules will be used. A grade  $\geq 3$  or adverse event that will lead to stop or termination of treatment is defined as suspected treatment related toxicity observed in the first 4 weeks of enrollment after dose modification, but excluding: nausea or vomiting and hematologic toxicities if not adequately treated. Ramucirumab will be held for drug related adverse events grade  $\geq 3$  until recovery to grade  $\leq 1$  and then resumed with a lower dose level -1 (6 mg/kg). If the grade  $\geq 3$  related adverse events does not resolve within 3 weeks of holding treatment, subject will be taken off the trial. In the case of prolonged or medically concerning grade 2 toxicity related to chemotherapy combination, treatment will be interrupted until

[figure not shown]

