# 6.1 Dose Modifications for Ramucirumab/placebo

Ramucirumab/placebo will be held for Grade  $\geq 3$  study drug related adverse events until recovery to Grade  $\leq 1$  and then resume with a dose reduction (level -1; 6 mg/kg) if site investigator evaluation relates toxicity to ramucirumab/placebo. If a second Grade  $\geq 3$  drug related adverse event is experienced and does not resolve within 2 weeks of the initial dose reduction, an additional dose reduction (level -2; 5mg/kg) will be made. If Grade  $\geq 3$  related adverse event does not resolve within 2 weeks of the second dose reduction, the subject will be taken off the trial.

Table 3. Modified dose of ramucirumab

Dose level	Ramucirumab
Starting dose	8 mg/kg
Level -1 dose reduction	6 mg/kg
Level -2 dose reduction	5 mg/kg

Version Date: 13AUG2018 Confidential Page 20 of 51

Table 4. Dosing level of ramucirumab/placebo for treatment related adverse events

Toxicity NCI	Worst Interval Toxicity	Day of Treatment
Grade (value)		
1	Maintain dose level	Continue treatment per protocol schedule.
2	Maintain dose level	Hold until resolved to grade 1 or less.
3	Reduce to dose level -1 6 mg/kg	Hold until resolved to grade 1 or less.
4	Reduce to dose level -2 5 mg/kg	Hold until resolved to grade 1 or less.

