# 6.1.6 Conditions for permanent discontinuation of ramucirumab/placebo

Listed below are clinical conditions in which ramucirumab/placebo should be permanently discontinued.

- Grade 3 and 4 arterial thromboembolic events, or any PE/DVT occurring or
  worsening during anticoagulant therapy. Any arterial event leading to
  discontinuation of ramucirumab therapy will be considered serious and should be
  reported via the serious adverse event (SAE) mechanism.
- Subjects with Grade 4 hypertension must not receive further treatment with ramucirumab
- Gastrointestinal Perforation
- Grade 3 or 4 Bleeding
- Grade 3 or 4 Infusion Reaction
- Hepatic encephalopathy or other serious signs of liver impairment such as hepatorenal syndrome
- Fistula Formation
- Reversible Posterior Leukoencephalopathy (RPLS); All cases of RPLS must be reported via the SAE reporting guidelines.

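### The synopsis and 11.6 restart ramucirumab at 6 mg/kg after any recovered related Grade 3 or higher event, without excepting the events after which 5.4.10 and Section 6 bar further drug

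*Combined protocol and SAP*

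**What the plan says.** The same restart rule appears in two places outside Section 6: the synopsis, under Statistical Considerations (early stopping), and 11.6. In both, ramucirumab is held for a related event of Grade 3 or higher until it improves to Grade 1 or less "and then resumed with a lower dose level -1 (6 mg/kg"). Each text then gives one exit for such events. In the synopsis it applies if the event "does not resolve within 3 weeks of holding treatment, subject will be taken off the trial"; in 11.6 it applies if the event "does not resolve within 4 weeks of holding treatment, the subject will be taken off study treatment". Neither text excepts any event or refers the reader to Section 6 or 5.4.10.

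Section 6.1.6 opens with "Listed below are clinical conditions in which ramucirumab/placebo should be permanently discontinued". Its list includes "Grade 3 or 4 Bleeding", and its first bullet begins "Grade 3 and 4 arterial thromboembolic events, or any PE/DVT occurring or" and goes on to cover clots that worsen under anticoagulation. The list also contains Grade 4 hypertension, Grade 3–4 infusion reaction, gastrointestinal perforation, fistula, serious liver impairment and RPLS. Section 5.4.10 repeats the bar for Grade 3–4 infusion reaction, 6.1.1 repeats it for Grade 4 hypertension, and 6.1.5 repeats it for clots that occur or worsen on therapeutic anticoagulation.

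The general rule at the head of 6.1 is also to hold "and then resume with a dose reduction (level -1; 6 mg/kg) if site investigator evaluation relates toxicity to ramucirumab/placebo". Table 4 has a separate entry for Grade 4: "Reduce to dose level -2 5 mg/kg". Section 5.1 names Section 6 as the place where dose modifications are set out.

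**The concern.** The two sets of instructions cannot both be followed for the same patient. The synopsis and 11.6 make the restart depend on grade, relatedness and recovery alone. Sections 5.4.10 and 6.1.1–6.1.6 identify events after which recovery does not matter and the drug is finished.

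What is at stake is re-exposure to ramucirumab/placebo after an event that the protocol itself treats as disqualifying. These events are foreseen in this trial. Section 9.1.5 lists hypertension, arterial thrombosis, hemorrhage and infusion reactions among the reported effects of ramucirumab. The interim safety table in 11.6.2, shortly after the restart sentence, sets stopping counts for hypertension, gastrointestinal perforation, bleeding and life-threatening thromboembolic events. A reader dealing with those toxicities therefore meets the unqualified restart rule close by.

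**Working it through.** No formula applies; the check is a comparison of texts.

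**Step 1. What each text directs after a related event that has recovered to Grade 1 or less within the hold limit.**

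| Event | Synopsis and 11.6 | Event-specific rule |
|---|---|---|
| Grade 3–4 bleeding | Resume at 6 mg/kg | Permanent stop (6.1.6) |
| Grade 3–4 arterial thromboembolism | Resume at 6 mg/kg | Permanent stop (6.1.6) |
| Grade 3–4 infusion reaction | Resume at 6 mg/kg | Permanent stop (5.4.10, 6.1.6) |
| Grade 4 hypertension | Resume at 6 mg/kg | Permanent stop (6.1.1, 6.1.6) |
| PE/DVT arising or worsening on anticoagulation, if Grade 3 or higher | Resume at 6 mg/kg | Permanent stop (6.1.5, 6.1.6) |
| GI perforation, fistula, RPLS, serious liver impairment, if Grade 3 or higher | Resume at 6 mg/kg | Permanent stop (6.1.6) |

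The first four rows name a grade in the discontinuation rule. The last two do not, so they collide with the restart rule only when the event reaches Grade 3. The table is not exhaustive: 6.1.1, 6.1.2 and 6.1.5 contain further permanent stops, for uncontrollable severe hypertension, for certain levels or recurrences of proteinuria, and for life-threatening or inadequately treated Grade 3/4 venous events.

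**Step 2. When the conflict arises.** The event must be Grade 3 or higher, judged drug related, and recovered in time. The limit is 3 × 7 = 21 days in the synopsis and 4 × 7 = 28 days in 11.6. Take a related Grade 3 bleed that recovers within 21 days. The synopsis and 11.6 both restart it at 6 mg/kg; 6.1.6 ends the drug. If the event does not recover in time, the patient comes off under every text and there is no conflict over restarting.

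**Step 3. Whether the synopsis and 11.6 can be read as short forms of Section 6, carrying its exceptions with them.** They do not match it on other points:

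| Item | Synopsis | 11.6 | 6.1 and Table 4 |
|---|---|---|---|
| Limit on the first hold | 3 weeks | 4 weeks | None stated; 2 weeks after the second reduction ends participation |
| Dose after Grade 4 | 6 mg/kg | 6 mg/kg | 5 mg/kg (Table 4) |

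Since they differ from Section 6 on the hold limit and on the Grade 4 dose, a reader has no basis for assuming that its exceptions are silently included.

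**Step 4. Whether any text settles the order.** Section 5.1 points to Section 6 for dose modification, and 6.3 refers to toxicity-related discontinuation as something already provided for. Neither says that the event-specific stops override the restart rule in the synopsis or 11.6.

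**The case against.** The best reply is that the protocol already resolves this. Section 5.1 assigns dose modification to Section 6. The stops in 5.4.10 and 6.1.1–6.1.6 are specific and absolute, and make sense only as limits on a general hold-and-resume rule. Neither the synopsis nor 11.6 could serve as dosing instructions: they give no starting dose or infusion rate, and the term for the reduced dose level is defined in Table 3 of 6.1. A site must open Sections 5 and 6 to give the drug at all.

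Most of this stands. Section 6 is very probably meant to govern, and a site that works from it is unaffected. What does not follow is that the synopsis and 11.6 are harmless summaries. They state a complete rule with its own exit, they depart from Section 6 on other points, and nothing subordinates them to it.

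A reader might go further and infer that 6.1 and Table 4 are themselves in conflict with 6.1.6. The documents do not support that. A default at the head of a section, followed by numbered event-specific subsections, is ordinary protocol structure, and the exceptions are in the same section.

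**Conclusion.** The point holds for the synopsis and 11.6 only. As written, both direct a restart at 6 mg/kg in patients for whom 5.4.10, 6.1.1, 6.1.5 or 6.1.6 requires that the drug be stopped for good. It is a wrong instruction in a safety rule and should be corrected. The exposure is narrow: the event must be related, Grade 3 or higher and recovered within the hold, and the reader must be relying on one of these two texts.

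The size cannot be put as a number of patients, because the documents give no rates for these events in this setting. Two other figures that a reader might infer should also be left out. One is a 29-day window under 6.1 and Table 4, taken from the rule that ends protocol therapy at an interruption of 30 days; that assumes that holding ramucirumab alone counts as interrupting protocol therapy, which the documents do not say. The other is a total count of conflicting conditions taken from 6.1.6, which would omit the further stops in 6.1.1, 6.1.2 and 6.1.5.

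Sample size, error rates and efficacy analyses are untouched.

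**What to change.** In the synopsis (early stopping) and in 11.6, directly after the resume rule, add: *except for conditions requiring permanent discontinuation of ramucirumab/placebo under 5.4.10 and 6.1.1–6.1.6, which take precedence*.

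A similar pointer in 6.1 and Table 4 would help the reader but is optional; nothing there needs correcting on this point. The cost is one clause in two places, with no added procedures, patients or analyses.
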